7.4 LOST TO FOLLOW-UP

For both the Single Ascending Dose and the Multiple Single Dose studies a subject will be considered lost to follow-up if he or she fails to return for a single visit and is unable to be contacted by the study site staff.

The following actions must be taken if a participant fails to return to the clinic for a required study visit:

- The site will attempt to contact the participant and reschedule the missed visit as soon as possible that same day and counsel the participant on the importance of maintaining the assigned visit schedule and ascertain if the participant wishes to and/or should continue in the study.
- If the missed visit consists of timed blood draws for PK and PD, that subject will be immediately considered lost to follow up and may be replaced.
- Should the subject be unreachable, he or she will be considered to have withdrawn from the study with a primary reason of lost to follow-up.

For both the Single Ascending Dose and Multiple Single Dose studies, subjects that are lost to follow up may be replaced. For the Single Ascending Dose study, and at least 6 (3M/3F) subjects/cohort will complete all aspects of the study. For the Multiple Single Dose study at least 8 (4M/4F) subjects will complete all aspects of the study.

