7.2 DISCONTINUATION OF STUDY INTERVENTION

Discontinuation from BIO 300 Oral Powder does not mean discontinuation from the study, and the remaining study procedures should be completed as indicated by the study protocol. If a clinically significant finding is identified (including, but not limited to changes from baseline) after enrollment, the Principal Investigator or qualified designee will determine if any change in participant management is needed. Any new clinically relevant finding will be reported as an adverse event (AE).

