7.3 PARTICIPANT DISCONTINUATION/WITHDRAWAL FROM THE STUDY

Subjects are free to withdraw from participation in the study at any time upon request. The Principal Investigator may discontinue or withdraw a subject from the study for the following reasons:

- Pregnancy (see **Section 8.4.8**). Women of childbearing potential must perform a pregnancy test in case of delayed menstruation and stop treatment immediately in case of positive result.
- Significant study intervention non-compliance.
- Any clinical adverse event (AE), laboratory abnormality, or intercurrent illness that, in the opinion of the Principal Investigator, indicates that continued participation in the study is not in the best interest of the participant.
- If the participant meets an exclusion criterion (either newly developed or not previously recognized) that precludes further study participation.
- If the participant withdraws their informed consent.

The reason for participant discontinuation or withdrawal from the study will be recorded on the Case Report Form (CRF). Subjects who sign the informed consent form and are randomized but do not receive the study intervention may be replaced.

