7.5 DOSE ESCALATION CRITERIA

A Safety Monitoring Committee (SMC) consisting of a Humanetics representative, the Medical Monitor and Principal Investigator, or their recognized delegates will review all available data. The determination for escalation to the next Cohort will require, at a minimum, a review of all safety data of 6 subjects in the previous SAD Cohort through at least Day 3. Decisions to proceed with dose escalations, adding additional subjects to the current Cohort, and possible dose adjustments will be made following this review with the Medical Monitor and Principal Investigator agreeing with the decision. Whether additional information such as PK or PD data may be needed before a decision to escalate can also be determined by the SMC. The primary responsibility of the SMC is to regularly monitor the overall safety of patients enrolled in the study, while protecting the scientific integrity of the study data. Dose escalation criteria will be the following:

- Dose escalation may occur if no more than 2 subjects in a 6-subject cohort experiences a dose-limiting toxicity (DLT, as defined below).
- If 3 DLTs occur (3/6 subjects), an additional 2 subjects will be treated with the same dose.
- If no additional DLTs occur (3/8 subjects), dose escalation may proceed.
- The study sponsor will temporarily cease enrollment for evaluation if in any given cohort 4/8 subjects experience DLTs attributable to BIO 300 Oral Powder as the MTD (maximum tolerated dose) will have been exceeded and no further dose escalation will occur.

DLT is any grade 3 or grade 4 adverse event listed in the draft FDA document entitled "*Toxicity Grading Scale for Healthy Adult and Adolescent Volunteers Enrolled in Preventive Vaccine Clinical Trials*."

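### Protocol 7.4 classes a reachable, already dosed subject who misses a timed PK and PD visit as lost to follow-up, which can end safety follow-up that other sections require

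*Combined protocol and SAP*

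**What the plan says.** Protocol 7.4 applies to both parts of the study. Its opening definition has two conditions: the subject "fails to return for a single visit and is unable to be contacted by the study site staff". Three bullets follow.

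- First bullet, any missed required visit: "The site will attempt to contact the participant and reschedule the missed visit as soon as possible that same day". The site also finds out whether the subject wishes to, or should, continue.
- Second bullet, a missed visit with timed PK and PD draws: "that subject will be immediately considered lost to follow up and may be replaced".
- Third bullet, no contact: "Should the subject be unreachable, he or she will be considered to have withdrawn from the study with a primary reason of lost to follow-up".

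Neighbouring sections bear on this:

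- Protocol 7.3 names only undosed subjects as replaceable: "Subjects who sign the informed consent form and are randomized but do not receive the study intervention may be replaced".
- Protocol 7.2 says that stopping the drug "does not mean discontinuation from the study, and the remaining study procedures should be completed".
- Protocol 7.5 makes escalation depend, at a minimum, on "a review of all safety data of 6 subjects in the previous SAD Cohort through at least Day 3".
- Protocol 8.2 collects AEs until 7 days after the last dose, and 8.4.4 follows all AEs to resolution.
- SAP 5.2 puts every subject with at least one dose in the safety dataset. SAP 7.2 rules out imputation.

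**The concern.** The second bullet treats a gap in the PK/PD record as a loss of the subject. Unreachable subjects have their own bullet, so the second one must also cover people the site can contact, and nothing limits it to undosed subjects.

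Safety is half of the primary objective. A missed timed draw makes a concentration profile incomplete, but it is no reason to stop looking for late laboratory or ECG changes in someone who has taken the drug. A site that acts on the label could reasonably stop scheduling that subject. The later safety results would then never exist, and membership of the safety dataset would not bring them back.

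A second gap follows. Once a dosed subject has been replaced, 7.5 does not say whether that subject belongs in the numerator and denominator of the DLT review.

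**Working it through.** **1. The plan's own count.** Protocol 1.1 and SAP 4 require at least 32 completers. Four SAD cohorts of 6 plus 8 in the multiple-dose cohort: 4 × 6 + 8 = 24 + 8 = 32, which agrees. The target counts completers and is silent on dosed subjects who are replaced.

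**2. Whom the second bullet reaches** (schedule of activities, Protocol 1.3, and the visit list in 8.3).

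| Visit | PK | PD | Already dosed if this visit is missed | Caught, read literally |
|---|---|---|---|---|
| SAD Day 1 | yes | yes | no | undosed only |
| SAD Day 2 | yes | yes | yes | **yes** |
| SAD Day 3 | yes | no | yes | no |
| SAD Day 8 | no | no | yes | no |
| Multiple-dose Day 1 | yes | yes | no | undosed only |
| Multiple-dose Day 6 | yes | yes | yes, up to 5 doses | **yes** |
| Multiple-dose Day 7 | yes | yes | yes, up to 6 doses | **yes** |
| Multiple-dose Day 8 | yes | no | yes | no |
| Multiple-dose Day 13 | no | no | yes | no |

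**3. Laboratory results at risk.** The blood-volume tables (Protocol 8.3.1 and 8.3.2) confirm the number of draws as total volume ÷ volume per draw.

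- SAD: CBC 9 ÷ 3 = 3, chemistry 10.5 ÷ 3.5 = 3, coagulation 8.1 ÷ 2.7 = 3. One set is at screening, so 3 − 1 = 2 are post-dose (Days 3 and 8). A subject declared lost at Day 2 and not seen again has 0 of 2.
- Multiple dose: CBC 12 ÷ 3 = 4, chemistry 14 ÷ 3.5 = 4, coagulation 10.8 ÷ 2.7 = 4. One is at screening, so 4 − 1 = 3 follow the start of dosing (Days 3, 6 and 13).
  - Declared lost at Day 6: 1 of 3 remains (Day 3). Note 5 to the schedule has chemistry drawn before dosing, so the last chemistry follows two doses in a subject who may have taken five.
  - Declared lost at Day 7: 2 of 3 remain, but the Day 6 chemistry precedes the sixth dose, so none follows it.

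Results from the missed visit itself are lost through absence. What the label puts at risk is the later visits: SAD Days 3 and 8; multiple-dose Days 7, 8 and 13 after a missed Day 6, or Days 8 and 13 after a missed Day 7. Days 3, 8 and 13 in those lists also carry vital signs, and SAD Days 3 and 8 and multiple-dose Day 13 carry ECG and physical examination.

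**4. The AE window.** Seven days after a Day 1 dose is Day 8; seven days after a Day 6 dose is Day 13. These are the final visits, so ending follow-up at Day 2 or Day 7 conflicts with the collection period in 8.2.

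**5. Counting in the DLT review.** Protocol 7.5 has rules for 6 and for 8 subjects. One replacement gives 6 + 1 = 7 dosed. Suppose 3 of the 7 had a DLT and one of the 3 was replaced. Counting all dosed subjects gives 3/7, for which there is no rule. Counting only the six who were not replaced gives 2/6, at which escalation may proceed. This shows that the reading depends on an unstated convention; it does not estimate how often the case would arise.

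**The case against.** **No sentence cancels later visits.** This is right. The first bullet of 7.4 requires contact for any missed visit, and 8.2 and 8.4.4 do not exempt subjects labelled lost. A reader might infer that the rule removes later safety data. The documents support only that it can, and the conflict between sections is the reason to clarify.

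**The reach is narrow.** A reader might count two of the three SAD follow-up visits as triggers because Day 3 has a PK sample. The bullet says PK and PD, and Day 3 has no PD draw, so only Day 2 qualifies.

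**Bias in escalation is not shown.** A reader might infer that one replaced subject, 1/6 = 16.7% of a cohort, turns 3/6 into 2/6 and lowers the DLT rate. That does not stand. Seven subjects would have been dosed, the review covers all available data with six as a minimum, and SAP 5.2 and the opening of SAP 9 keep observed data regardless of deviations. A DLT already observed, or reported at the same-day contact, is not clearly dropped. Illness as the reason for absence is possible, but no passage gives a rate.

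**The SAD cohorts appear to be finished.** The entry for version 2.0 in the amendment history (10.3) refers to Cmax from all four SAD cohorts. The escalation question is then largely one of reporting. The follow-up question stays live for the multiple-dose cohort.

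**Protocol 7.2 is weak support.** It concerns stopping the drug, not missing a visit. It shows only that the protocol elsewhere separates leaving treatment from leaving the study.

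What survives is the contradiction inside 7.4, its possible cost in safety data, and the missing counting rule.

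**Conclusion.** The point holds as a contradiction with a possible, unquantified consequence. The definition and the second bullet of 7.4 cannot both apply to a reachable dosed subject. If the label is acted on, that subject could have 0 of 2 post-dose laboratory sets (SAD, lost at Day 2) or no Day 13 assessment (multiple dose, lost at Day 6 or 7). The safety dataset keeps what was collected but cannot supply what was not, and nothing is imputed.

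This rests on two assumptions: that the bullet is read literally, and that a site would treat a subject declared lost as having no further visits. The documents give no missed-visit rate and do not say that replaced subjects are left out of the DLT review. The direction and size of any bias in AE or DLT rates therefore cannot be stated. The wording should be corrected because the gap is specific and the remedy cheap; there is no evidence that a completed escalation decision was wrong.

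**What to change.** 1. Reconcile the definition and second bullet of Protocol 7.4. A reachable dosed subject who misses timed draws is classed as PK/PD non-evaluable and may be replaced for PK/PD only. The subject remains in the safety visits already scheduled and in the safety and DLT summaries.
2. Reserve lost to follow-up for subjects who cannot be contacted, as the opening definition does.
3. Align 7.3, which names only undosed subjects as replaceable, with 7.4.
4. Reconcile 7.4 with 7.5 on how a dosed, replaced subject enters the DLT count, since 7.5 covers only 6 and 8 subjects. The sponsor and the Safety Monitoring Committee must settle the rule itself. For SAD cohorts already run, report dosed, replaced and completing subjects separately and state which denominator was used.
5. Reconcile the sentence in Protocol 9.4.1 that limits all analyses to those completing the treatment periods with SAP 5.2. A multiple-dose subject who misses Day 6 would fall under the first and be retained by the second.

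The cost is a wording amendment, the remaining safety visits for any replaced subject, and a counting rule for cohorts with a replacement. No new visit type or assay is needed.

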7.5 DOSE ESCALATION CRITERIA

A Safety Monitoring Committee (SMC) consisting of a Humanetics representative, the Medical Monitor and Principal Investigator, or their recognized delegates will review all available data. The determination for escalation to the next Cohort will require, at a minimum, a review of all safety data of 6 subjects in the previous SAD Cohort through at least Day 3. Decisions to proceed with dose escalations, adding additional subjects to the current Cohort, and possible dose adjustments will be made following this review with the Medical Monitor and Principal Investigator agreeing with the decision. Whether additional information such as PK or PD data may be needed before a decision to escalate can also be determined by the SMC. The primary responsibility of the SMC is to regularly monitor the overall safety of patients enrolled in the study, while protecting the scientific integrity of the study data. Dose escalation criteria will be the following:

- Dose escalation may occur if no more than 2 subjects in a 6-subject cohort experiences a dose-limiting toxicity (DLT, as defined below).
- If 3 DLTs occur (3/6 subjects), an additional 2 subjects will be treated with the same dose.
- If no additional DLTs occur (3/8 subjects), dose escalation may proceed.
- The study sponsor will temporarily cease enrollment for evaluation if in any given cohort 4/8 subjects experience DLTs attributable to BIO 300 Oral Powder as the MTD (maximum tolerated dose) will have been exceeded and no further dose escalation will occur.

DLT is any grade 3 or grade 4 adverse event listed in the draft FDA document entitled "*Toxicity Grading Scale for Healthy Adult and Adolescent Volunteers Enrolled in Preventive Vaccine Clinical Trials*."

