1 PROTOCOL SUMMARY

1.1 SYNOPSIS

Title:	A Phase 1 Dose Escalation Trial Evaluating the Safety and Pharmacokinetic Profile of BIO 300 Oral Powder in Healthy Volunteers
Study Description:	
Single Ascending Dose:
 
Open-label, single-dose escalation in healthy volunteers. Each cohort will enroll 8 subjects of which 2 will be backups (1M/1F), so that at least 6 subjects (3M/3F) complete the protocol procedures. The pertinent safety data will be reviewed for each cohort before the next dose level cohort is started. Subjects will follow a diet low in soy isoflavones for 7 days before and 7 days after treatment and will fast at least 8 h before dosing. The test article will be administered on day 1 and the initial dose will be one BIO 300 Oral Powder sachet, 500 mg genistein. Subsequent doses will be 2x the previous cohort. The fourth, and final cohort, dose level will be TBD based on the safety and pharmacokinetic (PK) results from the previous 3 cohorts. Subjects will remain in the clinic 12 hours after dosing for observations and blood sample collection for clinical lab assessment, PK, and pharmacodynamics (PD). Subjects will remain fasted for 4 hours after the test article administration. Subjects will be provided a standardized low soy meal after the 4-hour blood draw and after the 8-hour blood draw. Subjects will return to the clinic on day 2, 3 and 8 after dosing for blood sampling and/or observations as detailed in the schedule of events. Subjects may not miss any clinic visits. At the conclusion of the study, data will be analyzed from all cohorts to determine safety and PK. PD samples will be stored until the completion of all phase 1 studies, and then sent for RNA sequencing and data analysis.

Multiple Single Dose:

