Open-label, single dose given daily for 6 days in healthy volunteers. A single cohort will enroll 14 subjects (7M/7F) of which 4 will be backups (2M/2F), so that at least 8 subjects (4M/4F) complete the protocol procedures. Subjects will follow a diet low in soy isoflavones for 7 days before treatment, during the 6 days of treatment and 7 days after treatment. Subjects will fast at least 8 h before the first dose, 3rd dose and the 6th dose. The test article will be administered starting on day 1 and the dose used in this study will be determined based on safety and PK analysis from the single ascending dose study. Subjects will be administered test article daily during their schedule clinic visits. Subjects will remain in the clinic 4 hours after the first dose and 12 hours after the 6th dose for observations and blood sample collection for clinical lab assessment, PK and PD. Subjects will remain fasted for 4 hours after the test article administration on days 1 and 6. On the 6th day, subjects will be provided a standardized low soy meal after the 4-hour blood draw and after the 8-hour blood draw. Blood sampling and/or observations will be performed on dosing days 1-6 as described in the schedule of events. Subjects will return to the clinic on days 7, 8 and 13 after initial dosing for blood sampling and/or observations as detailed in the schedule of events. Subjects may not miss any clinic visits. At the conclusion of the study, data will be analyzed to determine safety and PK, and data will be analyzed from all cohorts to determine PD.

Objectives:

Primary Objectives:

- Determine the overall adverse event and PK profiles of single ascending doses of BIO 300 Oral Powder in healthy volunteers
- Determine the overall adverse event and PK profile of multiple doses of BIO 300 Oral Powder in healthy volunteers

Secondary Objectives:

- Determine the effects of single and multiple doses of BIO 300 Oral Powder on blood-based biomarkers
- Use a combination of the PK and PD profiles from the single and multiple doses of BIO 300 Oral powder to identify the putative BIO 300 Oral Powder human efficacious dose

Endpoints:

Primary

Evaluate the safety and pharmacokinetics of BIO 300 Oral Powder in Healthy Volunteers

Secondary

Characterize the expression of blood-based biomarkers

Study Population:

[figure not shown]

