6.1.2 DOSING AND ADMINISTRATION

Single Ascending Dose Cohorts:

Cohort 1 dose: one BIO 300 Oral Powder sachet, 500 mg genistein

Cohort 2 dose: two BIO 300 Oral Powder sachets, 1000 mg genistein (2X the dose of Cohort 1 in the absence of dose-limiting toxicity [DLT])

Cohort 3 dose: four BIO 300 Oral Powder sachets, 2000 mg genistein (2X the dose of Cohort 2 in the absence of DLT)

Cohort 4 dose: TBD based on the observed PK and AE profiles in the first 3 dose cohorts

All single dose cohorts will be administered the drug at the clinic under the supervision of the study personnel. Subjects will follow a diet low in soy isoflavones for 7 days before and 7 days after treatment and will fast at least 8 h before dosing. Subjects will remain fasted for 4 hours after the test article

administration. Subjects will remain in the clinic 12 hours after dosing. Subjects will be provided a standardized low soy meal after the 4-hour blood draw and after the 8-hour blood draw. The purpose of fasting is to standardize the effect of food on PK and PD markers.

Multiple Single Dose Cohort:

The cohort 5 dose will be dosed daily for 6 consecutive days at the highest dose or the maximum tolerated dose from the Single Ascending Dose cohorts. Subjects will consume the test article each day within +/- 2 hours of time when the first dose was administered and not within 1 hour before or after eating. The Day 6 dose will be administered during clinic visit 7 so that PK and PD blood draws can be timed after the dose.

Drinking of room temperature water only, (up to 240 mL) will be encouraged following administration of each BIO 300 Oral Powder sachet.

Subjects will follow a diet low in soy isoflavones for 7 days before treatment, during the 6 days of treatment and 7 days after treatment. Subjects will fast at least 8 h before the first dose, 3rd dose and the 6th dose. Subjects will remain in the clinic 4 h after the first dose and 12 hours after the 6th dose. Subjects will remain fasted for 4 hours after the test article administration on days 1 and 6. On the 6th day, subjects will be provided a standardized low soy meal after the 4-hour blood draw and after the 8-hour blood draw. The purpose of fasting is to standardize the effect of food on PK and PD markers.

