5.4. Pharmacodynamics (PD) Population

The PD Population will include all subjects who receive at least 1 dose of BIO 300 Oral Powder and have sufficient, valid serum samples to estimate key parameters for at least 1 of the days of sampling. PD summaries will be based on the PD population.

6. Safety Monitoring Committee

A Safety Monitoring Committee (SMC) will review safety and PK data (when available) during the conduct of the study. After each cohort in the SAD study, the SMC will make decisions on proceeding with dose escalation, adding additional subjects to the current cohort, and possible dose adjustments. The SMC may also recommend stopping the study, suspending enrollment or significant changes to the dosing regimen and/or enrollment if warranted by safety data. The SMC will immediately communicate this recommendation to Humanetics for review and determination of a final decision. SMC data reviews are

not considered interim analyses and do not necessitate adjusting of the alpha level for multiple statistical hypothesis tests.

7. Statistical Methods

Unless stated otherwise, the term “descriptive statistics” refers to the number of subjects (n), mean, median, standard deviation (STD), minimum (min), and maximum (max) and standard errors/confidence intervals for continuous response variables and distribution tables or histograms for discrete response variables. Min and max values will be rounded to the precision of the original value, means and medians will be rounded to 1 decimal place greater than the precision of the original value, and STDs will be rounded to 2 decimal places greater than the precision of the original value. Percentages will be rounded to the nearest whole number (zeros are not displayed) with values of “< 1%” and “> 99%” shown as necessary for values falling near the boundaries.

The computed change from baseline will be calculated for all measured variables and expressed as the mean change from baseline + STD of the change from baseline. Analysis of covariance will be used to compare dosage groups on “change from baseline” measures (with baseline measurement considered as an adjustment covariate).

Unless otherwise note, all data collected during the study will be included in data listings and will be sorted by study cohort, subject number and then by visit for each subject number.

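### Protocol Section 7.5 attaches the enrollment halt and the MTD-exceeded declaration to 4/8 DLTs, so the worse results 4/6, 5/6 and 6/6 bar escalation by implication but trigger neither

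*Combined protocol and SAP*

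**What the plan says.** Protocol Section 7.5 (Dose Escalation Criteria) has four numerical lines:

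- Up to 2/6: "Dose escalation may occur if no more than 2 subjects in a 6-subject cohort experiences a dose-limiting toxicity".
- 3/6: "If 3 DLTs occur (3/6 subjects), an additional 2 subjects will be treated with the same dose".
- 3/8: "If no additional DLTs occur (3/8 subjects), dose escalation may proceed".
- 4/8: "The study sponsor will temporarily cease enrollment for evaluation if in any given cohort 4/8 subjects experience DLTs attributable to BIO 300 Oral Powder". The same line gives the reason, that the MTD has been exceeded, and ends escalation.

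No line names 4/6, 5/6 or 6/6.

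The MTD is used again in Section 6.1.2, where cohort 5 is "dosed daily for 6 consecutive days at the highest dose or the maximum tolerated dose from the Single Ascending Dose cohorts". The synopsis (Section 1.1) adds for the same cohort that "the dose used in this study will be determined based on safety and PK analysis from the single ascending dose study". SAP Section 6 leaves cohort decisions to the Safety Monitoring Committee (SMC): "the SMC will make decisions on proceeding with dose escalation, adding additional subjects to the current cohort, and possible dose adjustments".

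**The concern.** The four lines describe a two-stage rule: six subjects, then two more if exactly three have a DLT. The halt and the MTD declaration sit only at the end of the second stage. A cohort that does worse in the first stage never enters the second, so it never meets the denominator on which the halt is written. The mandated response is therefore weaker at 67%, 83% or 100% DLTs than at 50%.

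Two things are at stake. The first is whether enrollment at that dose must pause. The second, and the more lasting, is whether the dose is formally above the MTD, because that label helps to define the dose given on six consecutive days to healthy volunteers in cohort 5.

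**Working it through.** **Step 1: list the outcomes.** The denominators in 7.5 are treated subjects: the count is 3/6 before the extra two are treated and 3/8 after.

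| Result | Action stated in 7.5 |
|---|---|
| 0/6, 1/6, 2/6 | may escalate |
| 3/6, then 3/8 | may escalate |
| 3/6, then 4/8 | temporary halt, MTD exceeded |
| 3/6, then 5/8 | not named; read here as covered by 4/8 |
| 4/6, 5/6, 6/6 | none; escalation barred only because neither permission is met |

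This gap in the rule depends on no assumed DLT risk.

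**Step 2: how often the gap is reached.** The plan states no operating characteristic for this rule, so there is no figure of its own to reproduce. The documents give no DLT risk either. I assume a risk p per subject, independent subjects, and one meaning of DLT in all four lines. With X ~ binomial(6, p):

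- No stated halt: P(X ≥ 4)
- Stated halt: P(X = 3) × [1 − (1 − p)²]
- Escalation permitted: P(X ≤ 2) + P(X = 3) × (1 − p)²

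In full at p = 0.3:

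- P(X ≥ 4) = 15 × 0.3⁴ × 0.7² + 6 × 0.3⁵ × 0.7 + 0.3⁶ = 0.0595 + 0.0102 + 0.0007 = 0.0705 (0.07047 before rounding)
- P(X = 3) = 20 × 0.3³ × 0.7³ = 0.1852
- Stated halt = 0.1852 × (1 − 0.49) = 0.0945
- Escalation = 1 − 0.0705 − 0.0945 = 0.8351 (from unrounded terms)
- Share of non-escalating results with no stated halt = 0.0705 / (0.0705 + 0.0945) = 43%

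| Assumed p | P(X = 3) | 4–6 of 6, no stated halt | 4/8 or 5/8, stated halt | May escalate | Share of non-escalating results with no stated halt |
|---|---|---|---|---|---|
| 0.1 | 0.0146 | 0.0013 | 0.0028 | 0.9960 | 31% |
| 0.2 | 0.0819 | 0.0170 | 0.0295 | 0.9535 | 37% |
| 0.3 | 0.1852 | 0.0705 | 0.0945 | 0.8351 | 43% |
| 0.4 | 0.2765 | 0.1792 | 0.1769 | 0.6439 | 50% |
| 0.5 | 0.3125 | 0.3438 | 0.2344 | 0.4219 | 59% |

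The two non-escalating probabilities are equal near p = 0.396. Above that, the branch without a stated halt is the more likely one. The share conditions on results that are rare at low p, so the absolute column should be read with it.

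**Step 3: look for the trigger elsewhere.**

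- Section 7.1 defines DLTs for stopping dosing but gives no cohort count.
- Section 10.1.2 allows suspension for unacceptable risk.
- Section 10.1.7 requires discontinuation if the sponsor, consulting the Medical Monitor, finds unreasonable and significant risk.
- SAP Section 6 lets the SMC recommend stopping or suspending enrollment.

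The last three rest on judgment. None of the four fixes a count or declares the MTD exceeded.

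**The case against.** **4/8 may mean four DLTs in a cohort of up to eight.** The synopsis enrolls eight per single-dose cohort, two of them backups, and once four of six have a DLT a completed eight cannot fall below 4/8. This is probably what the sponsor intends. It is not what 7.5 says. If enrolled subjects were the denominator, the first-stage count would already be 3/8, not 3/6.

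**Eight can be reached by other routes.** A reader might infer that only 3/6 can lead to eight treated subjects. The documents do not support that. The SMC may add subjects, Section 7.4 allows replacements, and cohort 5 plans at least eight completers. But none of these is prescribed after 4/6, and using one would mean dosing two more people at a dose already too toxic in order to reach the denominator.

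**The dose would not go up anyway.** A reader might infer that escalation could follow 4/6. It could not, since neither permission in 7.5 is met. Section 6.1.2 is stricter still: it makes the doublings for cohorts 2 and 3 conditional on there being no DLT. That stands, but the condition concerns the next dose. It says nothing about a halt, the MTD or cohort 5.

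**Judgment would catch it.** The next cohort waits for safety review, and under 7.5 the Medical Monitor and Principal Investigator must agree to escalation or added subjects. The powers in Step 3 also apply. This reduces the practical risk considerably, but it does not supply the mandatory response that 7.5 gives to a milder result.

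**The single-dose part is over.** Section 10.3 shows that version 2.0 used Cmax from all four single-dose cohorts. If the rules were followed, cohorts 1 and 2 had been cleared before 2000 mg was given, so only cohorts 3 and 4 could have fallen in the gap. The documents do not report the DLT counts, so the question is narrowed rather than closed.

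**Conclusion.** The point holds. As written, 4/6, 5/6 and 6/6 get no mandatory halt and no MTD declaration, while 4/8 gets both. Under the binomial assumptions the probability per cohort is small at low risk (0.1% at p = 0.1, 1.7% at p = 0.2) and substantial for a clearly toxic dose (17.9% at p = 0.4, 34.4% at p = 0.5). If 4/8 is taken to mean exactly four, 5/8 falls in the gap too, and the share at p = 0.3 rises from 43% to 53%.

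A reader might go further and infer that nothing would keep such a dose out of cohort 5. The documents do not support that, because the synopsis bases the cohort 5 dose on safety and PK analysis. The supportable statement is narrower: 7.5 does not formally exclude the dose, and its exclusion rests on judgment. At version 2.0 that eligibility question is the main remaining effect. It is worth correcting because the rule concerns participant safety and the correction is a matter of wording.

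**What to change.** In Section 7.5, replace the 4/8 trigger with: *four or more dosed subjects in a cohort, whether 6, 7 or 8 have been dosed*. Keep the existing temporary pause in enrollment for evaluation; it need not become an outright stop. State that the MTD is then exceeded and that the dose is not eligible for cohort 5. Align the no-DLT condition on the cohort 2 and 3 doses in Section 6.1.2 with 7.5, so that one escalation rule applies. Whether cohort 5 needs a boundary of its own is a separate decision for the sponsor.

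The cost is wording only, with no extra subjects or procedures. The probability of escalating is unchanged at every p, because only results that already bar escalation are affected. The probability of a mandatory halt becomes the sum of the two non-escalating columns:

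| Assumed p | Halt now | Halt after the change |
|---|---|---|
| 0.1 | 0.0028 | 0.0040 |
| 0.2 | 0.0295 | 0.0465 |
| 0.3 | 0.0945 | 0.1649 |
| 0.4 | 0.1769 | 0.3561 |
| 0.5 | 0.2344 | 0.5781 |

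The downside is some loss of discretion: at an assumed 20% DLT risk there is a 1.7% chance per cohort that a dose now left to judgment is formally excluded.
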